## 5.2 Analysis Sets

The analysis set for cardiodynamic ECG assessment are defined as follows (Table 1).

Table 1 Analysis sets for cardiodynamic ECG assessment

Analysis Set	Definition
Safety Analysis Set	All subjects enrolled in the study who receive at least 1 dose of study drug (tapinarof). Subjects will be analyzed as treated.
PK Analysis Set	All subjects who have at least 1 application of study drug and have at least 1 evaluable PK assay result. A value that is below the limit of quantification is considered evaluable.
QT/QTc Analysis Set	All subjects in the Safety analysis set with measurements at baseline as well as on-treatment with at least 1 post-dose time point with a valid

Analysis Set	Definition
	$\Delta QTcF$ value. The QT/QTc analaysis set will be used for the by-time point and categorical analyses of the cardiodynamic ECG parameters.
PK/QTc Analysis Set	All subjects who are in both the PK and QT/QTc analysis sets with at least 1 pair of post-dose PK and QTcF data from the same time point. The PK/QTc analysis set will be used for the concentration-QTc analysis.

#### 5.3 Baseline

Time-matched baseline will be derived from measurements on Day -1 and the morning (pre-dose) of Day 1 for all continuous ECG parameters. For T-wave and U-wave, baseline includes any findings observed in any replicates from the time point that constitute time-matched baseline derived from Day -1 measurements.

## 5.4 QT Correction Methods

The QT and RR value for each beat will be used for HR correction. Replicate ECGs will be extracted in up to 10 replicates from each nominal time point prespecified in the protocol. The median value from each extracted replicate from evaluable beats will be calculated, and then the mean of all available medians (minimum 3 medians) from a nominal time point will be used as the subject's reportable value at that time point.

The Fridericia's correction QTcF is defined as QTcF =  $QT/RR^{1/3}$ .

## 6 Analysis

The Study Day to be used for all analyses (including by-time point analysis, categorical analysis, concentration-QTc analysis, and method bias sensitivity analysis) in this SAP will be either Day 1 or Day 29, depending on which day the highest mean  $C_{max}$  is observed. Based on the PK of tapinarof, it is expected that the highest mean  $C_{max}$  is observed on Day 1 and in such case, the analysis will be performed with data from all subjects on Day 1.

If tapinarof  $C_{max}$  is observed on the Day not chosen for the analysis, as described above, in a substantial proportion of subjects, , a sensitivity analysis may be performed using the concentration-QTc model from data on both days. The geometric mean  $C_{max}$  values for tapinarof on Day 1 and Day 29 will be determined, respectively, and the population point estimate and its 2-sided 90% CI for the predicted  $\Delta QTcF$  interval at the geometric mean  $C_{max}$  will be obtained.

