1.2. Rationale for Study Design and Dose

This study includes a 29-day, open-label treatment phase in which subjects will receive tapinar of cream, 1% once daily for 29 days. Tapinarof cream has been investigated in prior studies at concentrations from 0.5% to 8.0% and at once and twice daily dosing frequencies. The 1% concentration applied once daily was chosen as the dose and dosing frequency to take forward in the clinical development program based on the data from the GSK Phase 2b clinical study in subjects with psoriasis (Study 203120). In that study, applications of tapinarof at concentrations of 0.5% and 1% applied once or twice daily were evaluated. Overall, both concentrations demonstrated an acceptable safety profile when applied once or twice daily. A once daily application regimen may reduce systemic exposure as the skin heals, thereby providing a better safety profile for a drug intended for long-term use to treat a chronic condition. Based on the efficacy and safety data from Study 203120, a regimen of 1% once daily was chosen as the tapinar of concentration and dosing frequency to be investigated in this study and intended for registration. Tapinarof has a unique PK profile whereby the highest plasma concentrations are observed in the first week of the treatment period followed by a subsequent decline to undetectable or near undetectable levels after multiple weeks of dosing. Accumulation of drug after multiple dosing has not been observed in any clinical study with tapinar of to date. The 29-day treatment phase was selected to ensure steady-state is achieved and to provide a treatment duration that allows for evaluation of safety in this population with extensive disease that has not been evaluated to date.

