3. STUDY DESIGN

3.1. Overall Design

This is a Phase 2a, multicenter, open-label study to evaluate the safety and PK of topical tapinarof cream in adults with extensive plaque psoriasis. The study will consist of three phases: Screening (up to 34 days), Treatment (29 days), and Follow-up (7-10 days).

At Day -1, eligible subjects will be enrolled into the study. During the treatment period beginning on Day 1 (Baseline), subjects will apply tapinarof cream, 1% to affected areas once a day for 29 days. Subjects will return to the clinic on Days 2, 15, 29, and 30 for study assessments and will receive a phone call on Days 8 and 22. Subjects will return to the clinic for a follow-up visit 7-10 days after the Day 29 visit. On clinic visit days, subjects will apply the study drug under the supervision of site personnel, after assessments have been completed. Full PK profiles and Holter monitoring will be collected on Day 1 and Day 29 (with corresponding 24-hour time points collected on Day 2 and Day 30, respectively). Limited PK sampling will be performed on Day 15. Pre-treatment, time-matched Holter monitoring will be conducted on Day -1 and the morning of Day 1.

Study drug will be dispensed to subjects during the clinic visits and will be administered at home between clinic visits as instructed by site personnel. Subjects will be instructed to apply study drug once daily to all affected areas, including newly appearing plaques and plaques/areas that improve during the study. Subjects will apply sufficient study drug to cover completely each lesion with a thin layer of study drug and will record the time of study drug application in a daily diary provided by the study site. Note that subjects are allowed, but not required, to treat palms, fingernails, soles, toenails, and scalp plaques with study drug. If a subject chooses to treat plaques on palms, fingernails, soles, toenails, and/or scalp, they should do so for the entirety of the treatment period from Day 1 to Day 29. Subjects will be instructed to apply study drug in the morning throughout the entirety of their participation in the study. At the phone contacts at Days 8 and 22, subjects should be reminded to complete their daily diary and bring it with them to the next clinic visit.

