10.4. Planned Analyses

All safety and PK measures over the course of the study will be presented. Details of planned analyses will be described in the statistical analysis plan (SAP) which will be finalized prior to database lock.

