### 3. STUDY OBJECTIVES

### 3.1 **Primary Objectives**

• To evaluate the safety and tolerability of tapinarof cream, 1% in adult subjects with extensive plaque psoriasis

Associated endpoints including:

- o Frequency and severity of adverse events (AEs) (local and systemic)
- Laboratory and biomarker values
- Vital signs
- Electrocardiograms (ECGs)
- o Mean Local Tolerability Scale (LTS) scores by visit
- To evaluate the pharmacokinetics (PK) of tapinar of cream, 1% in adult subjects with extensive plaque psoriasis

Associated endpoints including:

Tapinarof and tapinarof sulfate (metabolite) plasma PK parameters on Day 1 and Day 29, if data permit, including: area under the plasma concentration vs time curve in one dosing interval (AUC0- $\tau$ ), maximum plasma concentration (Cmax), time of maximum plasma concentration ( $t_{max}$ ) and elimination half-life ( $t_{1/2}$ ).

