## 3 Study Design

This is a Phase 2a, multicenter, open-label study to evaluate the safety and pharmacokinetics (PK) of topical tapinar fcream in adults with extensive plaque psoriasis. The study will consist of 3 phases: screening (up to 34 days), treatment (29 days), and follow-up (7-10 days).

At Day -1, eligible subjects will be enrolled into the study. During the treatment period beginning on Day 1 (baseline), subjects will apply tapinarof cream, 1% to affected areas once a day for 29 days. Subjects will return to the clinic on Days 2, 15, 29, and 30 for study assessments and will receive a phone call on Days 8 and 22. Subjects will return to the clinic for a follow-up visit 7-10 days after the Day 29 visit. On clinic visit days, subjects will apply the study drug under the supervision of site personnel, after assessments have been completed. Full PK profiles and Holter monitoring will be collected on Day 1 and Day 29 (with corresponding 24-hour time points collected on Day 2 and Day 30, respectively). Limited PK sampling will be performed on Day 15. Pre-treatment, time-matched Holter monitoring will be conducted on Day -1 and the morning of Day 1.

Subjects who withdraw from the study before Day 30 will complete an early termination visit. Study duration for subjects who complete this study is approximately 10 weeks in total.

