## 6.1 By-Time Point Analysis (Primary Analysis)

The QT/QTc analysis set on the selected Study Day, as described above, will be used for the by-time point analysis of cardiodynamic ECG parameters. The analysis for QTcF will be based on a linear mixed-effects model with  $\Delta$ QTcF as the dependent variable; time (i.e., post-baseline time point on the

Study Day: categorical), treatment (tapinarof), and time-by-treatment interaction as fixed effects. An unstructured covariance matrix will be specified for the repeated measures at post-baseline time points within subjects. If the model with an unstructured covariance matrix fails to converge, other covariance matrices such as compound symmetry and autoregressive will be considered. From this analysis, the least squares (LS) mean and 2-sided 90% CI for  $\Delta$ QTcF will be calculated at each post-baseline time point on the Study Day. If the upper bound of the 2-sided 90% CI lies below 10 ms for all post-baseline time points, tapinarof will be concluded not to have a clinically relevant effect on QT interval prolongation.

For HR, PR, and QRS intervals, the analysis will be based on the  $\Delta$ HR,  $\Delta$ PR, and  $\Delta$ QRS, respectively. The same (by-time point analysis) model will be used as described for QTcF. The LS mean, standard error, and 2-sided 90% CI from the statistical modeling for change-from-baseline values will be listed in the tables and graphically displayed.

The SAS code for the by-time point analysis for QTcF is as follows.

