## 6.2 Categorical Analysis

The QT/QTc analysis set on the Study Day will be used for the categorical analysis of cardiodynamic ECG parameters. Results for categorical outliers, T-wave morphology, and U-wave presence will be summarized in frequency tables with counts and percentages for both number of subjects and number of time points on the Study Day.

A subject or time point will be determined as an outlier if the following criteria (which are assessed separately) are met for the ECG intervals (Table 2).

Table 2 Criteria for determining a subject or time point outlier

ECG interval	Categorical outlier criteria
QTcF	Treatment-emergent value of $> 450$ and $\le 480$ ms when not present at baseline (new onset)
	Treatment-emergent value of $>$ 480 and $\le$ 500 ms when not present at baseline (new onset)
	Treatment-emergent value of > 500 ms when not present at baseline (new onset)
	Increase of QTcF from baseline of > 30 and ≤ 60 ms
	Increase of QTcF from baseline > 60 ms

ECG interval	Categorical outlier criteria
PR	Increase of PR from baseline > 25% resulting in PR > 200 ms
QRS	Increase of QRS from baseline > 25% * resulting in QRS > 120 ms
HR	Decrease of HR from baseline >25% resulting in HR < 50 bpm
	Increase of HR from baseline >25% resulting in HR > 100 bpm

\* In Section 10.4.3.3 of the protocol, it states a QRS increase from baseline >5%. This is an error in the protocol and it should be 25%.

All outliers will be summarized for each treatment group on the basis of incidence rates. If the subject experiences more than 1 episode of that event, then a subject will be counted only once for a particular outlier event. The total number of time points will be based on the number of observed time points across all subjects within a treatment group.

For T-wave morphology and U-wave presence, treatment-emergent changes will be assessed, i.e., changes not present at baseline. For each category of T-wave morphology and of U-waves, the category will be deemed as present when observed in any replicates at the time point. For baseline, the category will be deemed as present when observed in any replicates from all time points that constitute baseline.

The T-wave morphology and U-wave presence categories are described as follows (Table 3).

Table 3 T-wave morphology and U-wave presence categories (assessed manually)

Category Description	
Normal T-wave (+)	Any positive T-wave not meeting any criterion below.

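### The ECG plan confines the outlier, T/U-wave and HR/PR/QRS change tables to one Holter day, so about half of the on-treatment ECG time points are left out of the reported incidence

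*SAP*

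**What the plan says.** SAP Appendix D, section 6, begins "The Study Day to be used for all analyses (including by-time point analysis, categorical analysis, concentration-QTc analysis, and method bias sensitivity analysis" and defines that day by the higher mean Cmax, adding that Day 1 is expected.

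The limit is repeated for each analysis:

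- **Section 6.1 (by-time point):** "The QT/QTc analysis set on the selected Study Day, as described above, will be used for the by-time point analysis of cardiodynamic ECG parameters". HR, PR and QRS use the same model as QTcF, so they inherit the same day.
- **Section 6.2 (categorical):** outliers, T-wave morphology and U-waves are tabulated "with counts and percentages for both number of subjects and number of time points on the Study Day".

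The only analysis that may use both days is a concentration-QTc sensitivity analysis. It is optional and depends on a substantial proportion of subjects having their Cmax on the day not chosen.

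Holter ECGs are nevertheless planned for both Day 1 and Day 29, "with corresponding 24-hour time points collected on Day 2 and Day 30, respectively" (Appendix D, section 3). ECGs are listed among the endpoints of the primary safety objective (protocol section 2; SAP section 3.1). In the protocol text that can be read, the higher-Cmax day is attached only to the ΔQTcF endpoint (synopsis and section 2). The synopsis sentence on categorical outliers and section 10.4.3.2 on HR, PR and QRS name no day.

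**The concern.** Choosing the day of highest exposure suits a test that aims to exclude a QTcF effect. An incidence table has a different job: it tells the reader how many subjects had a marked ECG finding on treatment. Under the present rule, a new-onset QTcF above 500 ms, an increase above 60 ms or a new T-wave abnormality recorded on the other day would not be counted, and the table would give no sign of the omission.

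The second profile was not collected for nothing. Protocol section 1.2 states "The 29-day treatment phase was selected to ensure steady-state is achieved and to provide a treatment duration that allows for evaluation of safety". Day 29 is the only occasion on which the Holter schedule looks at the heart after repeated dosing, and under the expected choice that occasion drops out of the outlier, morphology and HR/PR/QRS summaries.

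**Working it through.** **Inputs.** From protocol Table 1 (footnotes c and d) and Appendix D, section 4: extraction before dosing and at 1, 2, 3, 4, 5, 8 and 12 h on Days 1 and 29, with the 24-h point on Days 2 and 30. From Appendix D, section 5.3: the Day 1 pre-dose ECG is part of baseline. From Appendix D, section 6.5: about 20 subjects. The documents give no figure of their own for this point, so there is none to reproduce.

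**Where the Day 2 ECG belongs.** It is the 24-h point of the Day 1 profile. On clinic days "subjects will apply the study drug under the supervision of site personnel, after assessments have been completed" (protocol section 3.1), so it precedes the second application.

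**Time points per subject.**

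- Day 1 profile: 7 post-dose + 1 at 24 h = 8.
- Day 29 profile: 7 post-dose + 1 at 24 h = 8, or 9 with the pre-dose ECG, which is on treatment by then.
- Post-dose total: 8 + 8 = 16. On-treatment total: 8 + 9 = 17.

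| Reading | Outside the tables | Share |
|---|---|---|
| Day 1 chosen, post-dose points only | 8 of 16 | 50% |
| Day 1 chosen, Day 29 pre-dose counted | 9 of 17 | 53% |
| Day 29 chosen, Day 29 pre-dose counted | 8 of 17 | 47% |
| Day 1 chosen but read as excluding the Day 2 ECG | 17 − 7 = 10 of 17 | 59% |

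Appendix D does not say whether the Study Day includes its 24-h point, which is why the last row is possible. With 20 subjects and no missing data, the second row is 20 × 9 = 180 of 20 × 17 = 340 subject-time points.

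**Effect on incidence.** One affected subject seen only on the other day:

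- counted: 1/20 = 5.0%, exact 95% CI 0.1% to 24.9%;
- not counted: 0/20, with upper exact limit 1 − 0.025^(1/20) = 16.8%.

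**Do other tables fill the gap?** Appendix D plans Tables 14.1.1, 14.1.2, 14.1.3.1 to 14.1.3.4 and 14.1.4 to 14.1.10, that is 1 + 1 + 4 + 7 = 13, and names no second day for any of them. The main SAP (Appendix C) reserves 14.3.5.3.1 to 14.3.5.3.13, also 13. The match suggests that no further ECG tables are intended. It does not prove it, because Appendix D also allows extra numbered tables for the sensitivity analysis and Appendix C permits minor changes to the index. The Screening and Follow-up 12-lead ECGs have a listing only (16.2.9.4.1).

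**Are the other day's data at least listed?** Appendix D, section 5.1, says that data from all enrolled subjects will be listed. The listing index in section 8.3 does not say that both days are included, and it refers back to sections 6.1 and 6.2, which are limited to the Study Day. So the data appear at most in listings.

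**The case against.** The one-day choice is reasoned and specified in advance. Protocol section 1.2 says that plasma concentrations are highest in the first week and then fall to undetectable or nearly so, without accumulation. Day 29 changes would be uncontrolled, at low expected exposure, and measured against a baseline about four weeks old. More time points also bring more chance outliers. All of this stands as support for testing QTcF on one day. It does not justify leaving a recorded outlier out of an incidence count. The day is chosen on the mean Cmax, and Appendix D itself foresees that a substantial proportion of subjects may peak on the other day.

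A clinically significant ECG finding could also reach the adverse event tables, since protocol section 8.1.1 counts clinically significant abnormal safety assessments as adverse events. This cover is partial: the documents do not say that central Holter readings go back to the investigator.

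Two stronger readings are tempting, and the documents do not support either.

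- **A breach of the protocol.** Protocol section 10.4 says "All safety and PK measures over the course of the study will be presented", but section 10.1 speaks of safety data being listed by subject, so listings may satisfy that sentence. The text of protocol section 10.4.3.3 and of Appendix D, section 4.2.2, cannot be read in this copy and might set the day.
- **ECG tables that describe only 1 of 29 applications because of this rule.** The count is right if Day 1 is chosen, but most of it comes from the sampling schedule. Holter recordings surround only applications 1 and 29, so tables for both days would still cover 2 of 29.

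**Conclusion.** The point holds as a matter of reporting. A stated rule, and not just missing detail, keeps about half of the on-treatment Holter time points (8 of 16 post-dose; 9 of 17 with the Day 29 pre-dose ECG) out of the outlier, T/U-wave and HR/PR/QRS change tables. The conditional concentration-QTc sensitivity analysis is the only exception, and it produces none of those tables. At this sample size, a single omitted subject is the difference between 5.0% and zero.

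The fractions assume that Day 1 is chosen, that its 24-h point on Day 2 is included, and that no ECG is missing. The documents give no rate at which outliers might occur on the other day, so no probability of a missed finding is offered. The one-day ΔQTcF endpoint comes from the protocol and is not disputed. The change should be made, but the primary QTcF conclusion does not depend on it.

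**What to change.** 1. Keep the higher-Cmax day, and the rule that the upper 90% confidence bound lies below 10 ms at every post-baseline time point, as the sole primary QTcF analysis.
2. Produce Tables 14.1.4 to 14.1.7 for both Holter days, each with its 24-h point, shown by day, with an added count of subjects affected at any time on treatment.
3. Give time-point percentages by day only. Pooling would dilute them: four outlier time points all on Day 1 are 4/160 = 2.5% by day but 4/340 = 1.2% pooled.
4. Add descriptive versions of Tables 14.1.2 and 14.1.3.1 to 14.1.3.4 for the other day.
5. State that the Study Day includes its 24-h point and that the ECG listings cover both days.
6. Add a footnote that Day 29/30 changes are uncontrolled and measured against a baseline about four weeks old.

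The cost is SAP wording and a little more programming on ECGs that are collected anyway. No visits or subjects are added, and the primary rule loses no power. The downside is some extra chance outliers, which the by-day display and the footnote let the reader weigh.

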## 6.1 By-Time Point Analysis (Primary Analysis)

The QT/QTc analysis set on the selected Study Day, as described above, will be used for the by-time point analysis of cardiodynamic ECG parameters. The analysis for QTcF will be based on a linear mixed-effects model with  $\Delta$ QTcF as the dependent variable; time (i.e., post-baseline time point on the

Study Day: categorical), treatment (tapinarof), and time-by-treatment interaction as fixed effects. An unstructured covariance matrix will be specified for the repeated measures at post-baseline time points within subjects. If the model with an unstructured covariance matrix fails to converge, other covariance matrices such as compound symmetry and autoregressive will be considered. From this analysis, the least squares (LS) mean and 2-sided 90% CI for  $\Delta$ QTcF will be calculated at each post-baseline time point on the Study Day. If the upper bound of the 2-sided 90% CI lies below 10 ms for all post-baseline time points, tapinarof will be concluded not to have a clinically relevant effect on QT interval prolongation.

For HR, PR, and QRS intervals, the analysis will be based on the  $\Delta$ HR,  $\Delta$ PR, and  $\Delta$ QRS, respectively. The same (by-time point analysis) model will be used as described for QTcF. The LS mean, standard error, and 2-sided 90% CI from the statistical modeling for change-from-baseline values will be listed in the tables and graphically displayed.

The SAS code for the by-time point analysis for QTcF is as follows.

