 - elimination half-life $(t_{1/2})$

- Analysis of change from Baseline in QTcF (Δ QTcF) at each post-treatment time point on the sampling day with the higher C_{max} (Day 1 or Day 29)
- Concentration-QTc analysis investigating the relationship between tapinar of plasma concentration and ΔQTcF, if data permit
- Mean change from Baseline to Day 29 in PGA, PASI, and %BSA

Statistical Methods:

Safety and PK data will be presented in tabular and/or graphical format and summarized descriptively.

For cardiodynamic ECG assessments, the primary analysis will be based on by-time point analysis to evaluate the effect of tapinarof cream, 1% on the $\Delta QTcF$ at each post-dosing time point using the Intersection Union Test. The effect of tapinarof on ΔHR , ΔPR , and ΔQRS will also be evaluated using the Intersection Union Test. An analysis of categorical outliers will also be performed for changes in HR, PR, QRS, QTcF, T-wave morphology and U-wave presence. In addition, a potential concentration-QTc analysis will be performed if a sufficient number of PK samples are measurable, i.e., above the lower limit of quantification, to provide a PK profile in most subjects. In this concentration-QTc analysis, the relationship between tapinarof plasma concentrations and $\Delta QTcF$ will be evaluated using a linear mixed-effects modeling approach.

PGA, PASI, and %BSA will be compared to Baseline values using a one sample t-test.

SCHEDULE OF ASSESSMENTS

Table 1: Schedule of Assessments

		Treatment Period (Tapinarof Cream, 1% Once Daily)						Follow-up		
Procedure	Screening (up to 34 days prior to Day 1)	Day -1	Baseline Day 1	Day 2	Day 8	Day 15	Day 22	Day 29	Day 30	(7-10 days after Day 29) or ET
	Visit 1	Visit 2	Visit 3	Visit 4	Phone Call	Visit 5	Phone Call	Visit 6	Visit 7	Visit 8
Informed consent	X									
Inclusion and exclusion criteria	X	X	X							
Demography	X									
Brief physical exam (including height, weight and BMI at Screening)	X									X
Medical history (including year of psoriasis diagnosis)	X									
Pregnancy test (WOCBP)	X		X							X
PGA, PASI, and % BSA evaluation ^a	X		X					X		
HIV, Hep B and Hep C Screen	X									
Laboratory assessments (chemistry including liver chemistries, hematology, urinalysis)	X		X					X		X
LTS assessment by Investigator			X			X		X		
Single 12-lead ECG	X									X
Continuous Holter Monitoring		X ^b	X ^c	X ^d				X ^c	X ^d	
Vital signs (pre-dose; HR, BP, and temperature)	X		X							X
Randomization			X							

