## 4 Cardiodynamic ECG Assessment

Continuous Holter recordings will be performed on Days –1, 1, 2, 29, and 30.

On Day -1, a Holter monitor will be attached for approximately 13 hours to collect pre-treatment, time-matched ECG data. Digital 12-lead ECGs will be extracted from the continuous recording at time points corresponding to time points on Day 1 and Day 29.

On Day 1 and Day 29, a Holter monitor will be attached 1 hour prior to dosing and for 12 hours post-dose. Digital 12-lead ECGs will be extracted at the same time points as PK samples, i.e., pre-dose and at 1, 2, 3, 4, 5, 8, and 12 hours post-dose.

On Day 2 and Day 30, a Holter monitor will be attached for 1 hour prior to the 24-hour post-dose PK time point to allow for extraction of 12-lead ECGs corresponding to the 24-hour post-dose PK time point.

Subjects will rest in a supine or semi-recumbent position for at least 10 minutes before and 5 minutes after each time point for ECG extraction. All ECG extractions will be performed immediately before the PK sample is drawn, when applicable.

All Holter/ECG data will be collected using M12R continuous 12-lead digital recorders and the M12A Enterprise Holter System Client (Global Instrumentation, LLC, Manlius, New York, USA). The equipment will be supplied and supported by

ECG intervals will be measured by the core laboratory in a blinded manner using the Expert Precision QT technique (EPQT) (see Appendix A for more details). The ECG database will be locked before any statistical analysis is undertaken.

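### If the unstructured QTcF model does not converge, the named fallback covariances pool one variance over all time points, so the upper bound behind the 10 ms rule would be too narrow at a noisier point

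*SAP*

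**What the plan says.** SAP Appendix D, 6.1 models change from baseline in QTcF by categorical time. "An unstructured covariance matrix will be specified for the repeated measures at post-baseline time points within subjects". If that model does not converge, "other covariance matrices such as compound symmetry and autoregressive will be considered". Protocol 10.4.3.2 has the same fallback. Neither document gives an order, a rule for choosing, a robust standard error, or a statement on whether the equal-variance or the heterogeneous versions are meant. The SAS code announced in 6.1 does not appear in the text available.

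The bound from this model decides the QT conclusion. Absence of a clinically relevant effect is concluded "If the upper bound of the 2-sided 90% CI lies below 10 ms for all post-baseline time points". The protocol synopsis describes the same logic as testing "at each post-dosing time point using the Intersection Union Test", so every time point must pass and each test carries a one-sided 5% error.

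Appendix D, section 4 sets the ECG times on the dosing day at "pre-dose and at 1, 2, 3, 4, 5, 8, and 12 hours post-dose". The 24-hour value comes from the next day, when "a Holter monitor will be attached for 1 hour prior to the 24-hour post-dose PK time point". Section 6.5 gives about 20 subjects and no SD for the change in QTcF.

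**The concern.** The unstructured model lets each time point have its own variance. Standard compound symmetry and standard first-order autoregressive do not: both fit one variance for all times. Moving to either therefore changes the standard error at each time point as well as simplifying the correlations.

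The rule depends on upper bounds, so the direction matters. Where the true SD exceeds the pooled value, the bound is too low, and a real effect at that time is more likely to be declared absent. The choice of structure would also be made with the data in hand. At stake is the study's secondary objective of excluding a clinically relevant QTcF effect.

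**Working it through.** The documents give no power, SD or derived sample size for this analysis, so there is no figure of the plan's to reproduce. The check compares the bound under a pooled variance with the bound under a separate variance.

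**Inputs from the documents**
- n = 20 (Appendix D, 6.5).
- Eight post-dose times: 1, 2, 3, 4, 5, 8, 12 and 24 h (Appendix D, section 4). This counts the 24-hour value with the selected day.
- Margin 10 ms and two-sided 90% CI, that is one-sided 5% (Appendix D, 6.1).

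**Assumptions**
- SD 8 ms at seven times and 10, 12, 14 or 16 ms at one time.
- Complete data.
- Within-subject correlation 0.5 in the simulations of the rule, unless stated otherwise.

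**Step 1: standard errors.** With complete data and categorical time, the LS mean at each point is the raw mean under every structure. Only the standard error changes:
- Separate variance: SE = SD_t/√n.
- Compound symmetry: SE = SD_pool/√n, where SD_pool = √(mean of the eight variances).

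For a noisier SD of 12 ms, SD_pool = √((7×64 + 144)/8) = √74 = 8.60 ms. The standard error there is 8.60/12 = 0.72 of its true value.

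**Step 2: half-width and false-pass rate.** With t(0.95, 19 df) = 1.729 and √20 = 4.472, the half-width is 1.729×SD/4.472. For a true mean of exactly 10 ms at the noisier point, the chance that its bound falls below 10 ms is approximately Φ(−1.729×SD_pool/SD_t).

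| SD at noisier point (ms) | SD_pool (ms) | SE ratio | Correct half-width (ms) | Pooled half-width (ms) | Approximate false-pass rate |
|---|---|---|---|---|---|
| 10 | 8.28 | 0.83 | 3.87 | 3.20 | 7.6% |
| 12 | 8.60 | 0.72 | 4.64 | 3.33 | 10.8% |
| 14 | 8.97 | 0.64 | 5.41 | 3.47 | 13.4% |
| 16 | 9.38 | 0.59 | 6.19 | 3.63 | 15.5% |

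Simulating the full rule over all eight points, with 10 ms at the noisier point and 0 elsewhere, gives about 8%, 11%, 14% and 15–16% under compound symmetry. A separate variance per point stays near 5%. Using pooled residual degrees of freedom (19×8 = 152) raises the compound-symmetry rates by about one percentage point. First-order autoregressive behaves much the same: its SE ratios are 0.82–0.84, 0.71–0.73 and 0.58–0.61 at SD ratios 1.25, 1.5 and 2.0.

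**Step 3: quieter points.** At an SD of 12 ms for the noisier point, the standard error at the other seven is 8.60/8 = 1.08 times its true value. With the 10 ms effect at one of those points, the false-pass rate falls to 3.4%.

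**Step 4: spacing.** The gaps are 1, 1, 1, 1, 3, 4 and 12 h. With equal true variances, a first-order autoregressive model fitted to such data recovers the variance (ratio 1.000 in the limit, 1.001 on average at n = 20). The correlation is wrong, but the width of the bound is not.

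**Step 5: trigger.** The unstructured matrix has 8×9/2 = 36 parameters. With complete data its REML estimate is the sample covariance, which was positive definite in 5,000 of 5,000 simulated sets of 20 subjects. In a rough check by maximum likelihood (EM, not REML) with values deleted, 150 of 150 fits converged at 5% missing and 123 of 150 at 10%.

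**Step 6: does a heterogeneous structure repair it?** In 1,500 runs per case with exchangeable correlation, heterogeneous compound symmetry gave a 24-hour miss rate of 5.2% at SD ratios 1.5 and 2.0, against 11.6% and 15.3% for standard compound symmetry. With correlation decaying at 0.8 per hour it gave 2.9%, which is conservative.

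**The case against.** The strongest reply is that several conditions must hold together.

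- **Trigger.** The fallback applies only after non-convergence, which is unlikely with complete data. This stands. A reader might infer from 36 parameters and 20 subjects that failure is to be expected; Step 5 does not support that. But incomplete data are possible: one valid post-dose value admits a subject to the QT/QTc set, nothing is imputed, and replacement of withdrawals is optional.
- **Unequal variance.** No SD by time point is given. A reader might infer that the 24-hour point must be noisier because "extraction of 12-lead ECGs corresponding to the 24-hour post-dose PK time point" relies on a separate one-hour recording. The documents do not establish this. Baseline is drawn from Day -1 and pre-dose Day 1, so on Day 1 the 1 to 12 h changes also compare separate recordings on different days. Rest, position and extraction method are the same throughout. Unequal variance stays an assumption.
- **Effect pattern.** Inflation appears when the effect sits at the noisier point alone. With the noisier point at 24 h (SD 10 to 14 ms) and 10 ms at both 12 h and 24 h, the false-pass rate is 1.4–1.6%. With 8 ms elsewhere and 10 ms at 24 h it is about 1.3%. With 10 ms only at 4 h it is 3.1–4.1%. This stands and limits the finding.
- **Wording.** The list of fallbacks is open and does not exclude heterogeneous versions. That is correct, and it is a reason to name them.

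**Conclusion.** The point holds conditionally. If the unstructured model fails and a standard compound symmetry or autoregressive structure replaces it, and if one time point is noisier than the average, the deciding bound at that point is too narrow. For an effect at that point, the false-pass rate under compound symmetry is about 8%, 11% and 14% at SDs of 10, 12 and 14 ms against 8 ms elsewhere, with n = 20 and complete data. Quieter points err the other way. With equal SDs there is no loss of error control.

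The SDs are assumptions. The rates depend mainly on the SD ratio, and the half-widths in ms scale with the 8 ms. The rates were computed on complete data, while the trigger is mainly missing data, so they show the size of the mechanism and do not predict this trial's error rate.

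A reader might also infer that autoregressive's equal-spacing assumption narrows the bound. With complete data it does not; its effect with missing data was not quantified. Nor do the documents support saying that the planned QT conclusion is invalid, because the first-choice model is sound on this point. The change is still worth making: the fallback feeds a decision rule, is left open, and names structures that discard the feature of the unstructured model that keeps each bound correct.

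**What to change.** In SAP Appendix D, 6.1, replace the fallback sentence with a fixed order of structures that keep a separate variance per time point:

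1. Heterogeneous Toeplitz (8 variances + 7 correlations = 15 parameters).
2. Heterogeneous autoregressive or heterogeneous compound symmetry, with one of them named in advance (8 + 1 = 9 parameters).
3. As a last resort, a one-sample t 90% CI at each time point, which needs no convergence.

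Drop the equal-variance forms. A spatial power structure would handle the unequal spacing but would not restore separate variances, so it does not replace this list. Because Protocol 10.4.3.2 carries the same fallback, record the change among the changes to protocol-specified analyses.

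The cost is one sentence and one code option. If variances are in fact equal, the intervals are slightly less stable and a little wider: at SD 8 ms, 1.729×8/4.472 = 3.09 ms against 1.655×8/4.472 = 2.96 ms with 152 pooled degrees of freedom, about 0.1 ms. The t intervals ignore within-subject information when time points are missing. They equal the unstructured result only with complete data and no baseline covariate. The SAP model has no such covariate, but the model in Protocol 10.4.3.2 does.
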